6.5.7.2. Eliciting and Recording Adverse Events

Eliciting Adverse Events

The patient and legal guardian, if applicable, should be asked about medically relevant changes in the patient’s health since the last visit. The patient and legal guardian, if applicable, should also be asked if the patient has been hospitalized, had any accidents, used any new medications, or changed concomitant medication routines (both prescription and over-the-counter). In addition to patient observations, AEs will be documented from any clinically relevant laboratory findings, physical examination findings, ECG changes, or other findings that are relevant to patient safety.

Recording Adverse Events

The Investigator is responsible for recording non-serious AEs that are observed or reported by the patient after administration of the first dose of study drug regardless of their relationship to study drug through the end of study. Non-serious AEs will be followed until the end of study. Events occurring after signing of the ICF and before study drug administration will be captured as medical history (see Section 6.1), while AEs that occur after study drug administration, and baseline events that worsen after study drug administration, must be recorded as AEs.

The Investigator is responsible for recording SAEs that are observed or reported by the patient after the time when the informed consent is signed regardless of their relationship to study drug through the end of study. SAEs will be followed until satisfactory resolution, until baseline level is reached, or until the SAE is considered by the Investigator to be chronic or the patient is stable, as appropriate.

All AEs must be recorded in the source records for the clinical study center and in the eCRF for the patient, whether or not they are considered to be drug-related. Each AE must be described in detail: onset time and date, description of event, severity, relationship to study drug, action taken, and outcome (including time and date of resolution, if applicable).

For SAEs, record the event(s) in the eCRF and, as applicable, the SAE form.

All IRRs will be recorded as AEs. All information on IRRs is to be recorded on the applicable eCRF per the CRF completion guidelines.

If patients develop ocular symptoms suggestive of vitamin A deficiency, for example reduced night vision or night blindness, the Investigator should consult with the Medical Monitor to determine if an ophthalmological assessment is needed. Any information collected during an ophthalmological assessment should be recorded in the eCRF and reports or images of ophthalmological assessments should be collected as well.

6.5.7.3. Reporting Adverse Events of Clinical Interest to Sponsor/Designee

Not applicable. There were no AEs of Clinical Interest identified for this study.

6.5.7.4. Serious Adverse Events Require Immediate Reporting to Sponsor/Designee

An assessment of the seriousness of each AE will be made by the Investigator. Any AE and laboratory abnormality that meets the SAE criteria in Section 6.5.7.1 must be reported to the Sponsor or designee within 24 hours from the time that clinical study center staff first learns of the event. All SAEs must be reported regardless of the relationship to study drug.

The initial report should include at least the following information:

- Patient's study number
- Description and date of onset of the event
- Criterion for serious
- Preliminary assignment of relationship to study drug, and
- Investigator/site information

To report the SAE, complete the eCRF and, as applicable, the SAE form. Within 24 hours of receipt of follow-up information, the Investigator must update the eCRF and, as applicable, the SAE form. SAEs must be reported using the contact information provided in the Study Reference Manual.

Appropriate remedial measures should be taken by the Investigator using his/her best medical judgment to treat the SAE. These measures and the patient's response to these measures should be recorded. All SAEs, regardless of relationship to study drug, will be followed by the Investigator until satisfactory resolution or the Investigator deems the SAE to be chronic or stable. Clinical, laboratory, and diagnostic measures should be employed by the Investigator as needed to adequately determine the etiology of the event.

6.5.7.5. Sponsor Safety Reporting to Regulatory Authorities

The Sponsor or its representative will report certain study events in an expedited manner to the Food and Drug Administration, the European Medicines Agency's EudraVigilance electronic system according to Directive 2001/20/EC, and to all country Regulatory Authorities where the study is being conducted, according to local applicable regulations.

6.5.7.6. Serious Adverse Event Notification to the Institutional Review Board/Independent Ethics Committee

Suspected unexpected serious adverse reactions (SUSARs) will be reported to the IRB/IEC per their institutional policy by the Investigator or Sponsor (or Sponsor designee) according to country requirements. Copies of each report and documentation of IRB/IEC notification and acknowledgement of receipt will be kept in the Investigator's study file.

6.5.7.7. Pregnancy Reporting

If a female patient becomes pregnant during the study through 12 weeks following the last dose of study drug, the Investigator must report the pregnancy to the Sponsor or designee within

24 hours of being notified of the pregnancy. Details of the pregnancy will be recorded on the pregnancy reporting form. The patient should receive any necessary counseling regarding the risks of continuing the pregnancy, the possible effects on the fetus, and be counseled to not breastfeed for 12 weeks after the last dose of study drug.

The pregnancy should be followed by the Investigator until completion. At the completion of the pregnancy, the Investigator will document the outcome of the pregnancy. If the outcome of the pregnancy results in a postpartum complication, spontaneous abortion, stillbirth, neonatal death, or congenital anomaly, then the Investigator should follow the procedures for reporting an SAE as outlined in Section 6.5.7.4.

6.5.7.8. Overdose Reporting

An overdose is defined as any dose administered to or taken by a patient (accidentally or intentionally) that exceeds the highest daily dose, or is at a higher frequency, than included in the protocol. In the event of an overdose, the actual dose administered must be recorded as specified in the Pharmacy Manual.

All reports of overdose (with or without an AE) must be reported within 24 hours following the instructions outlined in the Pharmacy Manual for reporting an overdose.

6.5.8. COVID-19 Data Collection

Information on the COVID-19 infection status of the patient, if known, and other information on the impact of the COVID-19 pandemic on the patient's participation in the study will be collected.

6.6. Biomarkers and Biospecimen Repository

Alnylam's RNAi therapeutics platform permits the highly specific targeting of investigational therapies based on genetic sequence. It is possible that variations in the target genetic sequence will result in variations in drug effect. More generally, genetic variations may account for the well-described heterogeneous manifestations of disease in patients with ATTR amyloidosis with cardiomyopathy, as well as their responses to treatment.

Where allowed per local regulations, ethics committee (IRB/IEC) approval, and patient consent, samples will be collected as part of this study to permit exploratory investigations and the application of novel approaches to bioanalyses that may further elucidate the outcomes of this study, or potentially advance understanding of the safety, mechanism of action, and/or efficacy of patisiran.

Biological specimens will be collected at the intervals indicated in the Schedule of Assessments (Table 1, Table 2, Table 3, and Table 4). Potential exploratory investigations may include RNA or biochemical metabolite assessments as they relate to disease progression, efficacy or safety.

The biospecimen repository will also include residual material from routine samples (safety laboratory samples, PK samples, etc.) that are obtained during the study.

These specimens will be securely stored in a central biorepository for up to 10 years following the completion of this clinical study (ie, last patient last visit), or as per local regulations. After 10 years have elapsed, samples will be destroyed.

Details regarding the collection, processing, storage, and shipping of the samples will be provided in the Laboratory Manual.

Exploratory analysis of these biospecimens will be performed by Alnylam Pharmaceuticals or its designees.

When biobanking is permitted by local regulation, study participants will be advised during the informed consent process of these biobanking details and the potential for exploratory investigation of their samples.

7. STATISTICS

A Statistical Analysis Plan (SAP) will be finalized before database lock. The plan will detail the implementation of the statistical analyses in accordance with the principal features stated in the protocol.

7.1. Determination of Sample Size

The planned enrollment for this study is 300 patients. For the change from baseline at Month 12 in the 6-MWT, assuming a treatment difference of 33 meters between patisiran and placebo in the treatment-naïve group and 20 meters in patients with baseline tafamidis, the weighted average treatment difference between patisiran and placebo in the overall population is approximately 29 meters (standard deviation = 75 meters) assuming 70% are in the treatment-naïve group and 30% are in the baseline tafamidis group. A sample size of 300 patients provides >90% power for a 2-sided test to detect a mean difference between treatment groups at a 2-sided alpha = 0.05. Additional patients may be enrolled based on a recommendation to increase the sample size in the interim assessment (Section 7.2.10).

7.2. Statistical Methodology

The statistical and analytical plans presented below are brief summaries of planned analyses for the primary analysis, conducted at the completion of the 12-month, double-blind period. More complete plans, including planned analyses for the open-label extension period, will be detailed in the SAP. Changes to the methods described in the final SAP will be described and justified as needed in the clinical study report. For information on study endpoints, see Section 2.

Additional data summaries to help understand any impact of COVID-19 on efficacy and safety assessments will be outlined in the SAP.

7.2.1. Populations to be Analyzed

The populations (analysis sets) are defined as follows:

- Full Analysis Set (FAS): All randomized patients who received any amount of study drug, grouped according to the randomized treatment arm.
- Safety Analysis Set: All patients who received any amount of study drug, grouped according to the treatment actually received.

- PK Analysis Set: All patients who received at least 1 complete dose of study drug and have at least 1 postdose blood sample for PK parameters and have evaluable PK data.
- PD Analysis Set: All patients who received at least 1 complete dose of study drug and who have an evaluable baseline and at least 1 evaluable post-baseline serum TTR measurement will be included in the PD analyses.

Note that a complete dose of study drug is defined as $\geq 80\%$ (≥ 160 mL) of the planned infusion volume (200 mL).

Efficacy endpoints will be analyzed using the Full Analysis Set. Safety will be analyzed using the Safety Analysis Set. The PK and PD Analysis Sets will be used to conduct PK and PD analyses, respectively.

7.2.2. Examination of Subgroups

Subgroup analyses may be conducted for selected endpoints. Detailed methodology will be provided in the SAP.

7.2.3. Handling of Missing Data

Handling of missing data will be described in the SAP.

7.2.4. Baseline Evaluations

Demographics and other disease-specific baseline characteristics will be summarized by treatment arm and overall for the FAS and Safety Analysis Set.

7.2.5. Efficacy Analyses

The overall Type I error rate will be strongly controlled at a 2-sided 0.05 significance level for the primary and secondary endpoints using a fixed sequential testing procedure at the final analysis. The primary endpoint will be compared between treatment arms at the 0.05 significance level. If the test of the primary endpoint is statistically significant, then the secondary endpoints will each be tested in the order specified in the Secondary Endpoints section (see Section 2). If a test of the primary or a secondary endpoint is not statistically significant, the testing of the remaining endpoints in the sequence will stop.

For patients who were tafamidis treatment-naïve at baseline and start tafamidis during the double-blind period, the primary analysis of the primary endpoint will censor data collected after the initiation of tafamidis treatment post-randomization.

7.2.5.1. Primary Endpoint

The primary endpoint, change from baseline at Month 12 in the 6-MWT, will be analyzed using a mixed-effects model repeated measures (MMRM) approach. The outcome variable is change from baseline in the 6-MWT. The model will include the baseline value as a covariate, treatment, visit, baseline tafamidis (yes vs no), genotype (hATTR vs wtATTR), age (<75 vs ≥ 75 years), the treatment-by-visit interaction, the treatment-by-baseline tafamidis interaction, the visit-by-baseline tafamidis interaction, and the treatment-by-visit-by-baseline tafamidis

interaction as fixed factors. The primary comparison is the contrast (difference in least squares [LS] means) between the patisiran and placebo groups at Month 12.

Sensitivity analyses will be detailed in the SAP.

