3.5. Method of Assigning Patients to Treatment Groups

Using the interactive response system (IRS), patients will be randomized 1:1 to the patisiran or placebo arm. Randomization will be stratified by:

1. Baseline tafamidis (yes vs no)
2. Genotype (hATTR vs wtATTR amyloidosis with cardiomyopathy)
3. NYHA Class I or II and age < 75 years vs all other

Each patient will be uniquely identified in the study by a combination of the site number and patient identification number. Upon signing the informed consent form (ICF), the patient will be assigned a patient identification number by the IRS. The Investigator or his/her designee will contact the IRS to randomize the patient after confirming that the patient fulfills all the inclusion criteria and none of the exclusion criteria.

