7.2.5.2. Secondary Endpoints

Secondary endpoints are described in Section 2.

KCCQ-OS will be analyzed using a similar MMRM model as used for the primary endpoint.

The composite endpoint of all-cause mortality, frequency of CV events (CV hospitalizations and urgent HF visits) and change from baseline in 6-MWT will be analyzed using a generalized rank-based win ratio method, which makes pairwise comparisons (for all possible patisiran/placebo patient pairs) of the 3 components in the hierarchical order specified above. The point estimate for the win ratio is defined as the total number of better outcomes divided by the total number of worse outcomes in the patisiran group. The detailed algorithm for assessment of this endpoint will be provided in the SAP.

The composite endpoint of all-cause mortality and frequency of all-cause hospitalizations and urgent HF visits will be analyzed using a modified Andersen-Gill model stratified by baseline tafamidis (yes vs no), including treatment, genotype (hATTR vs wtATTR), NYHA Class (I/II vs III), and age (<75 vs \geq 75 years) as covariates.

Patients who undergo a heart transplantation and/or ventricular assist device placement after randomization will be handled in the same manner as death in the primary analyses of mortality related endpoints.

Deaths and hospitalizations due to COVID-19 will be excluded from the primary analyses of endpoints involving all-cause death and/or all-cause hospitalizations. Analyses of the individual components of the composite endpoints will be detailed in the SAP.

To control the overall Type I error rate, secondary endpoints will be tested in a prespecified hierarchical order.

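### The primary MMRM gives baseline 6-MWT one slope for Months 6, 9 and 12; a baseline-by-visit term would protect the Month 12 contrast at almost no cost

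*Protocol*

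**What the plan says.** Protocol section 7.2.5.1 lists the terms of the primary model: "The model will include the baseline value as a covariate, treatment, visit, baseline tafamidis (yes vs no"), followed by genotype, age group, treatment-by-visit, treatment-by-baseline tafamidis, visit-by-baseline tafamidis and the three-way term. The tafamidis interactions concern tafamidis use at baseline, not baseline walking distance. The synopsis gives the same list. The tested comparison is the difference in LS means at Month 12.

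Section 7.2.5.2 says: "KCCQ-OS will be analyzed using a similar MMRM model as used for the primary endpoint". It itemises no terms for that model.

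Section 7.2.5 censors 6-MWT data after a tafamidis-naïve patient starts tafamidis. Section 7.2.3 leaves missing-data handling to the SAP, and 7.2.5.1 leaves sensitivity analyses to it.

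**The concern.** The outcome is change from baseline. Its regression slope on baseline at visit t is (correlation with baseline × SD at t / SD at baseline) − 1. That slope changes between Months 6 and 12 if the correlation falls or the spread changes without the two offsetting each other. The model lets the treatment and tafamidis effects vary by visit but holds the baseline slope constant. If the true slopes diverge, the common slope is a compromise that need not suit Month 12, the only visit in the confirmatory test.

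Two things are at stake. The first is precision at Month 12. The second is bias, but only if the patients still contributing data differ between arms in baseline walking distance, so that the misfit no longer cancels. The primary test gates every secondary endpoint.

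**Working it through.** **The plan's own figure.** Inputs from section 7.1: "assuming a treatment difference of 33 meters between patisiran and placebo in the treatment-naïve group and 20 meters in patients with baseline tafamidis"; "assuming 70% are in the treatment-naïve group and 30% are in the baseline tafamidis group"; "in the overall population is approximately 29 meters (standard deviation = 75 meters"); "2-sided alpha = 0.05"; "A sample size of 300 patients provides >90% power for a 2-sided test". From section 3.5: "patients will be randomized 1:1 to the patisiran or placebo arm".

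- Weighted effect: 0.7 × 33 + 0.3 × 20 = 29.1 m.
- SE: 75 × √(2/150) = 8.66 m.
- Power: Φ(29/8.66 − 1.96) = 91.8%; 91.9% with 29.1 m; 91.6% by noncentral t.

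The stated power reproduces. It is a two-sample calculation without baseline adjustment, so the baseline term does not touch it.

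**Assumptions, not in the protocol.** Baseline SD 100 m; SD of change 55, 65 and 75 m at Months 6, 9 and 12; correlations 0.55-0.7; the slope and dropout patterns in the table.

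**Precision by hand, complete data.** Let b be the true Month 12 slope and c the fitted common slope. The variance of the contrast is (2/150) × [75² − b²·100² + (b − c)²·100²]. With the interaction the last term vanishes:

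- b = −0.20: √[(2/150) × (5625 − 400)] = 8.35 m.
- b = −0.30: √[(2/150) × (5625 − 900)] = 7.94 m (simulated 7.93).

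The simulated common-slope SEs of 8.47 and 8.31 m imply (b − c)·100 ≈ 12.5 and 21.3, so c is about −0.075 and −0.087. In both cases the common slope lies well short of the Month 12 slope.

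**Simulation.** The protocol's fixed effects and an unstructured covariance were fitted by maximum likelihood to 120,000 simulated patients, with SEs scaled to N = 300. SEs are for complete data. Bias is the common-slope estimate minus the interaction-model estimate; positive values favour patisiran. Losses are placebo/patisiran.

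| Slopes M6/M9/M12 | SE common vs interaction (m) | Bias, equal loss 16%/16% | Bias, loss 18%/13% (type I error) | Bias, placebo-only strong, about 24%/13% (type I error) |
|---|---|---|---|---|
| −0.10 throughout | 8.59 vs 8.59 | 0.0 m | 0.0 m (5.0%) | 0.0 m (5.0%) |
| −0.08/−0.10/−0.13 | 8.54 vs 8.53 (+0.1%) | 0.0 m | +0.4 m (5.0%) | +1.0 m (5.1%) |
| −0.05/−0.10/−0.20 | 8.47 vs 8.35 (+1.4%) | −0.2 m | +1.2 m (5.2%) | +3.0 m (6.3%) |
| 0/−0.15/−0.30 | 8.31 vs 7.93 (+4.8%) | +0.1 m | +1.8 m (5.5%) | +5.7 m (9.8%) |

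Type I error is Φ(−1.96 + bias/SE) + Φ(−1.96 − bias/SE). For a bias of 1.75 m and an SE of 8.86 m this is 0.0390 + 0.0155 = 5.45%.

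With missing data, the excess SE of the common-slope model was 1.0-1.5% for the moderate slopes and 5.1-5.6% for the large ones. The largest power loss was about 2.7 points (93.4% to 90.7%).

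**A second set of assumptions.** With baseline SD 105 m, about 8% dropout and 700 trials per scenario, the SE ratios (with/without the interaction) were:

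- 1.000 for slopes of −0.20 throughout;
- 0.998 for −0.12/−0.15/−0.20;
- 0.988 for −0.15/−0.20/−0.30;
- 0.965 for −0.10/−0.20/−0.35.

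With higher placebo dropout the common-slope model averaged 29.35 and 29.68 m for a true 29 m, against 29.00 and 29.01 m with the interaction. Each mean carries a Monte Carlo error of about 8/√700 = 0.3 m, so these agree in direction but add little on size.

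**The case against.** **Diverging slopes are not established.** A falling correlation steepens the slope, but a growing follow-up SD flattens it: 0.80 × 1.00 − 1 and 0.75 × 1.067 − 1 both give −0.20. The 150 m entry threshold may restrict baseline spread, and the disease is progressive, so offsetting is possible. This stands, and every statement about size is conditional on it.

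**A reader might infer that baseline-related dropout by itself biases the contrast, or that the model necessarily loses precision.** Neither follows. Equal dropout gave −0.2 to +0.1 m because the misfit cancels between randomised arms, and equal slopes cost nothing.

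**A reader might also take the 3-6 m biases and 9.8% type I error as expected.** They need moderate or large slope change together with strong baseline-related loss in placebo alone. The protocol predicts no such loss and partly guards against it. Exclusion criterion 8 keeps out naïve patients expected to start tafamidis, and section 4.3.1 encourages patients who stop study drug to stay for a Modified Month 12 visit. Censoring at drop-in could still produce imbalance, since section 5.3.1 leaves drop-in to investigator judgement and section 7.2.10 recognises its threat to power. No rates are given.

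**The SAP could add the term.** Section 7.2 calls its text a summary with fuller plans to follow. But 7.2.5.1 states the fixed-effect list outright, and section 7 requires the SAP to follow the protocol's principal features. That makes the common slope a stated specification rather than an omitted detail. For KCCQ-OS the objection succeeds: no terms are fixed there, so there is nothing to correct yet.

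**Conclusion.** The point holds as a minor, conditional improvement. The written model imposes one baseline 6-MWT slope on three visits while testing only the last. Unless the slopes diverge strongly, the cost is 0-1.5% of the Month 12 SE; strong divergence costs about 4-6%. Material bias requires diverging slopes and arm-differential, baseline-related missingness together: about 0-1.8 m against 29 m, with type I error of 5.0-5.5%, under modest imbalance (18% vs 13%).

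No figure in the protocol is wrong, and N = 300 with power above 90% stands. The sizes rest on an assumed baseline SD, assumed slopes and assumed dropout; the conditions under which each effect appears do not.

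**What to change.** Add the baseline 6-MWT-by-visit interaction to the fixed effects in section 7.2.5.1 and in the synopsis. When the KCCQ-OS model is specified, give it the matching baseline KCCQ-OS-by-visit term.

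The cost is 2 degrees of freedom in about 300 patients. With equal slopes the SE was unchanged under complete data, equal loss and modestly unequal loss. Under strong placebo-only loss it rose from 9.17 to 9.21 m (about 0.5%), and when baseline-related loss ran in opposite directions in the two arms, from 9.20 to 9.33 m (1.4%). The term does not address missingness that depends on unobserved walking distance; that remains a matter for the sensitivity analyses left to the SAP.

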For the change from baseline at Month 12 in the 6-MWT, assuming a treatment difference of 33 meters between patisiran and placebo in the treatment-naïve group and 20 meters in patients with baseline tafamidis, the weighted average treatment difference between patisiran and placebo in the overall population is approximately 29 meters (standard deviation = 75 meters) assuming 70% are in the treatment-naïve group and 30% are in the baseline tafamidis group. A sample size of 300 patients provides >90% power for a 2-sided test to detect a treatment difference at a 2-sided alpha = 0.05. Additional patients may be enrolled based on a recommendation to increase the sample size in the interim assessment.

The primary endpoint, change from baseline at Month 12 in the 6-MWT, will be analyzed using a mixed-effects model repeated measures (MMRM) approach. The outcome variable is change from baseline in the 6-MWT. The model will include the baseline value as a covariate, treatment, visit, baseline tafamidis (yes vs no), genotype (hATTR vs wtATTR), age (<75 vs ≥75 years), the treatment-by-visit interaction, the treatment-by-baseline tafamidis interaction, the visit-by-baseline tafamidis interaction, and the treatment-by-visit-by-baseline tafamidis interaction as fixed factors. The primary comparison is the contrast (difference in least squares [LS] means) between the patisiran and placebo groups at Month 12.

To control the overall Type I error rate, secondary endpoints will be tested in a prespecified hierarchical order.

For patients who are tafamidis treatment-naïve at baseline and start tafamidis during the double-blind period, the primary analysis of the primary endpoint will censor data collected after the initiation of tafamidis treatment post-randomization.

Safety data will be summarized descriptively.

Figure 1: Study Design

[figure not shown]

Table 1: Year 1 Schedule of Assessments: Double-blind Period (Screening to Month 12 Efficacy Assessments)

Table 1: Year 1 Schedule of Assessments: Double-blind Period (Screening to Month 12 Efficacy Assessments)

Study Day ±Visit Window	For Details see Section	Screen- ing		Baseline		Double-blind Treatment Period																																										
		V1	V2	Pre- dose	Post- dose																																											
		Day -45 to Day -1		Day 1																																												

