The 6-MWT will be performed at each of the timepoints specified in the Schedule of Assessments ([Table 1](#), [Table 2](#), [Table 3](#), and [Table 4](#)). At screening Visit 1, the 6-MWT will be administered for study eligibility purposes (per inclusion Criterion 6 [Section 4.1]). At screening Visit 1, prior to conducting the 6-MWT, the site staff will familiarize the patient with the purpose and conduct of the 6-MWT, as described in detail in the relevant study manual. Familiarization can be repeated at other timepoints if deemed helpful.

On Day 1 (baseline), which is a dosing day, the 6-MWT will be performed prior to study drug administration. (No other dosing days have a 6-MWT assessment.)

Patients who are hospitalized during the study should wait at least 2 weeks after hospitalization before completing a 6-MWT assessment; less time post-hospitalization may be permitted if, in the opinion of the Investigator, the patient is unencumbered due to the recent hospitalization. In addition, if a patient is not feeling well due to an external factor (eg, flu, sprained ankle, pulled

back muscle) at a visit when the 6-MWT will be performed, the test should not be done and should be rescheduled for another day within the permitted visit window.

For each 6-MWT assessment, the site should make every effort to have this assessment performed by the same assessor and to perform the test at approximately the same time of day. If the test is interrupted or deemed unusable by the 6-MWT core laboratory, the 6-MWT should be repeated as soon as possible within the allowed visit window.

Further details regarding the 6-MWT are provided in the relevant study manual.

A 1.5-month window will be used to group 6-MWT assessments to the Month 6 (Weeks 25-26), Month 9 (Weeks 37-38), and Month 12 (Weeks 52-53) visits. During the double-blind period, a patient may opt to begin tafamidis treatment or to discontinue study treatment, in which case they would complete a Pre-tafamidis Drop-in Visit ([Table 1](#)) or Early Treatment Discontinuation Visit ([Table 4](#)), respectively. To avoid the potential training effect from repeated assessments of the 6-MWT within a short period of time, only one 6-MWT assessment should be collected for the following time periods: Day 2 to Day 214 (for Month 6), Day 215 to Day 319 (for Month 9), and Day 320 to Day 417 (for Month 12).

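### Free improvement, low severity: each patient walks two 6-MWTs before the first dose, and the primary MMRM adjusts for only the Day 1 walk

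*Protocol*

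**What the plan says.** Section 6.2.1 describes two walks before treatment. "At screening Visit 1, the 6-MWT will be administered for study eligibility purposes", and inclusion criterion 6 makes a walk of at least 150 m a condition of entry. Then, "On Day 1 (baseline), which is a dosing day, the 6-MWT will be performed prior to study drug administration". Section 3.1 allows up to 45 days for screening.

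Section 7.2.5.1 lists the primary model terms: "The model will include the baseline value as a covariate, treatment, visit, baseline tafamidis (yes vs no"), genotype, age group and the interactions of treatment, visit and baseline tafamidis. The synopsis gives the same list: "The model will include the baseline value as a covariate". No screening 6-MWT appears in either place. Section 7.2.5.1 leaves sensitivity analyses to the SAP but states the covariates itself, and Amendment 3 revised that covariate list in the protocol.

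On size, section 7.1 says "A sample size of 300 patients provides >90% power for a 2-sided test", based on a difference of "approximately 29 meters (standard deviation = 75 meters").

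**The concern.** A single effort-dependent walk measures a patient's capacity with error. The protocol recognises this: section 6.2.1 asks for the same assessor and time of day, reschedules for passing illness and limits repeat walks because of training. The Day 1 error enters every change score, and one covariate cannot remove all of it. A second walk by the same method, taken before randomisation, would be expected to carry some further information about the Month 12 result.

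The primary test gates the whole fixed sequence in section 7.2.5, so its standard error matters. Section 7.1 states no allowance for missing Month 12 walks, section 4.3.4 does not replace patients who stop, and section 7.2.5 censors walks after tafamidis drop-in. Section 7.2.10 itself expects that drop-in could cost power and contemplates enrolling more patients. Recovering precision from data in hand is cheaper than enlarging the trial.

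**Working it through.** **Inputs from the protocol (sections 3.5 and 7.1).** 300 patients, 1:1, so 150 per arm; two-sided alpha 0.05; SD 75 m; difference about 29 m, from 0.7 × 33 + 0.3 × 20 = 29.1 m.

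**Inputs not in the protocol, assumed.** Correlation of a pre-dose walk with Month 12: rho = 0.60 to 0.80. Correlation between the two pre-dose walks: r0 = 0.85 to 0.95. One check on rho: if 75 m is the SD of change and the 6-MWT has equal spread at both visits with an assumed SD S, then rho = 1 − 75²/(2S²), which is 0.65 at S = 90 m and 0.80 at S = 120 m.

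**Step 1: the plan's own figure.** Standard error = 75 × √(2/150) = 8.66 m. Power = Φ(29/8.66 − 1.96) = Φ(1.39) = 91.8%. The stated figure reproduces. Power of 90% needs 141 per arm, 282 in all, so the margin is 18 patients with complete data.

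**Step 2: the gain.** The share of Month 12 residual variance that the screening walk removes is its squared partial correlation with Month 12 given Day 1. Write rho_s and rho_d for the correlations of the screening and Day 1 walks with Month 12:

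g = (rho_s − rho_d·r0)² / [(1 − rho_d²)(1 − r0²)]

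If both walks correlate equally with Month 12, this becomes

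g = rho²(1 − r0) / [(1 − rho²)(1 + r0)]

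At rho = 0.70 and r0 = 0.90: 0.49 × 0.10 / (0.51 × 1.90) = 5.1%. Over the assumed range:

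| rho | r0 = 0.85 | r0 = 0.90 | r0 = 0.95 |
|---|---|---|---|
| 0.60 | 4.6% | 3.0% | 1.4% |
| 0.70 | 7.8% | 5.1% | 2.5% |
| 0.80 | 14.4% | 9.4% | 4.6% |

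If the screening walk correlates 0.02 less with Month 12 than Day 1 does, the range becomes 0.2 to 10.0%. If rho_s = rho_d·r0, the gain is zero.

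**Step 3: a repeated-measures check.** A simulated MMRM with Months 6, 9 and 12, unstructured covariance and a common baseline slope gave gains of 1.6 to 5.1% across five assumed covariance structures.

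**Step 4: what the gain is worth.** Taking 75 m as the residual SD, the new SD is 75 × √(1 − g) and the equivalent sample size is 300/(1 − g).

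| g | SD | Power at 29 m | Equivalent N |
|---|---|---|---|
| 0 | 75.0 m | 91.8% | 300 |
| 1% | 74.6 m | 92.0% | 303 |
| 5% | 73.1 m | 93.0% | 316 |
| 14% | 69.6 m | 95.1% | 349 |

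The protocol does not say whether 75 m is the SD of change or a residual SD. If it is the SD of change, with equal spread at both visits, adjusting for Day 1 alone multiplies the variance by (1 + rho)/2. Starting power is then above 91.8%, and the gain in power points is smaller.

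**The case against.** The strongest reply is that nothing here is wrong. The model is a standard, unbiased, baseline-adjusted MMRM and the power claim reproduces. That stands in full, and it is why this is a suggestion and not an error.

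Section 7.2 also calls its text a brief summary, with fuller plans in the SAP. That carries less weight, because section 7.2.5.1 and the synopsis list the model terms one by one.

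A reader might infer that the plan forfeits a definite amount, say 3 to 12% of the variance. A measurement-error calculation can produce that: with single-walk error SDs of 20, 30 and 40 m, a between-patient SD of 100 m and an SD of change of 75 m, the gains are 3.4%, 7.1% and 11.8%. But the protocol gives neither the error SDs nor the between-patient SD, and the calculation treats screening as an exact replicate of Day 1. The screening walk is the first one, just after familiarisation and up to 45 days earlier. Allowing learning to vary between patients with an SD of 20 to 30 m (also an assumption) lowers the gains to 1.6–2.2%, 4.7–5.8% and 9.1–10.4%. A learning shift common to all patients does no harm when screening is a separate covariate.

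A reader might also infer that the trial is underpowered without this change. The documents do not support that: a figure below 90% needs a rate of missing Month 12 walks that the protocol does not state.

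**Conclusion.** The point holds as a modest, free gain in precision. Two pre-dose walks exist for every enrolled patient and the primary model uses one. Under the assumed correlations the unused walk accounts for about 1 to 14% of the Month 12 residual variance. Near 5%, it is worth 93.0% power against 91.8%, or 300/0.95 − 300 ≈ 16 patients, close to the 18-patient margin found in Step 1. The gain could be close to nothing if the screening walk adds little once Day 1 is known. No bias and no type I error problem is claimed against the present model. Severity is low.

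**What to change.** In section 7.2.5.1 and in the synopsis, add the screening Visit 1 6-MWT as a second continuous covariate beside the Day 1 value, and keep the outcome as change from the Day 1 baseline. Because a test can be repeated (section 6.2.1) and a patient can be rescreened (section 6.1.2), name the value to use: the last valid screening walk.

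The cost is one phrase in each place, one model term and about one degree of freedom. No visit, procedure or patient is added. Type I error is unaffected because the covariate precedes randomisation, provided the term is prespecified before unblinding.
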